Although the intervention was well-received (80.4% would recommend it to others), modalities were not fully integrated and engagement declined over time. To better understand why engagement may have declined, we interviewed 38 participants (n=20 intervention; n=18 control) throughout the final months of the study. Participants in both study groups reported using non-study designed, consumer-level devices and apps to help them meet their weight-loss goals (e.g., Fitbit and MyFitnessPal). Additionally, although Facebook emerged as the primary modality through which dynamic content was delivered at the group level and over half (56%) of participants had at least one Facebook friend in the study, intervention participants expressed a desire for greater online interaction with other participants. This finding aligns with our preliminary quantitative analysis of online communication about weight-related behaviors. Specifically, intervention participants spoke more about PA and diet with their existing online social networks than did control participants. Furthermore, a 20% increase in social support for talking about PA and diet on Facebook (defined as likes and comments) was associated with a weight loss of 4.1 kg from baseline to 6 months among female participants. Taken together, these findings suggest that an intervention that incorporates popular consumer-level devices and apps, while also capitalizing on existing and study-engineered social networks, may be highly engaging to young adults.

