## **8. RESEARCH DESIGN AND METHODS**

### **Overview**

The SMART 2.0 study is a 24-month (96 week) parallel-group randomized control trial designed to evaluate the efficacy of the intervention with technology and personal health coaching or with technology alone to improve objectively measured weight in kg over 24 months compared to a control group. We will recruit 642 overweight/obese young adults aged 18-35 at the University of California, San Diego (UCSD), San Diego State University (SDSU) and California State University, San Marcos (CSUSM) in San Diego. Participants will be assigned to one of three groups for a 24-month study period. The three groups include:

1. SMART 2.0 with technology, social media, and personal health coaching (T1)
2. SMART 2.0 with technology and social media alone (T2)
3. Control group

SMART 2.0 improves upon its predecessor by using a fully integrated system of modalities that includes 1) a popular consumer-level wearable activity tracker (Fitbit Charge 3), wireless scale (Aria Scale), and apps (Fitbit); 2) a highly tailored and interactive text messaging system (described in detail below); 3) multiple social media streams including Facebook, Facebook Messenger, Instagram and Twitter, and 4) enhanced social network mechanisms of influence. Consumer-level devices and apps will be used to self-monitor behavior, and their data will be passively acquired in real-time. Algorithms will be used to automatically deliver interactive text messages to support individually tailored goal setting, performance feedback, and goal review in a highly dynamic style that reflects participants' behavioral progress towards achieving a minimum goal of 5% weight loss. Participants will be encouraged to share their data and behavioral progress with others via social networking tools built into the apps. Social network mechanisms of influence will be used both within the study-space, to elicit participant-to-participant and health coach-to-participant support, as well as outside the study-space, to invoke social support and accountability from strong ties known to be important for long-term behavior change. Additionally, one group will receive monthly technology-mediated, real-time personal health coaching that is theory- and evidence-based.

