### Consumer-level wearable and scale: Fitbit Charge 3 and Aria Scale

**Figure 1.** Fitbit Charge 3

A Fitbit Charge 3 (<https://www.fitbit.com/charge3>) and Fitbit Aria 2 scale (<https://www.fitbit.com/aria2>) will be provided to all participants in the study. The Fitbit Charge 3 is not considered to be a medical device or a significant risk device. It is made of flexible, durable elastomer material similar to that used in many sport watches, and it has a surgical grade stainless steel buckle. It is lightweight (1.06 oz), 0.5 inches wide, and fits wrists that are 5.4 to 8.7 inches in diameter. It contains a triaxial accelerometer, an optical heart rate monitor, an altimeter, and a vibration motor.

All participants will have the ability to monitor physical activity, sleep and diet with the Fitbit Charge 3 and weight with the Aria scale. Additionally, participants in both intervention groups (T1 and T2) will receive feedback on physical activity, sleep, diet activity, and weight collected through these devices via SMS messaging, as described in the following section.

Data from the devices will be passively and securely streamed to the Fitbit website. It will then be retrieved using software developed by Small Step Labs, LLC and Fitabase Inc (<https://www.fitabase.com>) and stored securely on their servers. All data that is subsequently downloaded from Fitabase Inc. servers for analytic purposes will remain de-identified and will be stored on secure, password-protected CPHS/EPARC servers. There are two instances when researchers will contact Fitabase Inc. in order to delete data associated with participants in this study: 1) anytime that a participant chooses to withdraw from the study and 2) at the completion of the study (when all data analysis has been completed). Researchers will contact [name], CEO of Small Step Labs, LLC and creator of Fitabase ([[contact]](mailto:[contact])) and he will initiate a deletion of the data from live servers and all data will be phased out of offline backups within 90 days. After 90 days Small Step Labs will have no data associated with the study on their servers.

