**Table 4. Example of weekly text messages to be used in SMART 2.0 intervention**

Day of the Week	Timestamp	Message Type	Message
Sunday	12pm	Sleep Feedback	You reached your weekly sleep goal by getting an average of 6 hrs 30 min a night. Keep it up and try to get in 6 hrs 50 min per night. Make sure to

			wear your Fitbit for at least 4 nights to get a better picture of your sleep patterns this week.
Sunday	7pm	Sleep Tip	Sleep tip: Try reading from a book or using a blue light filter on your laptop/phone when studying or reading before bedtime.
Monday	12pm	Exercise Feedback	Good work getting in 110 active minutes last week. But, your goal was to complete 140 minutes. Try to set a new goal of 130 minutes for this week. You can do it!
Tuesday	12pm	Diet Feedback	Terrific job tracking your calories this month. On average, you are eating as much as you burn. To lose 1 lb, you should be in a deficit of 500 calories per day. Continue to make progress by tracking consecutively for 3 days this month!
Tuesday	7pm	Diet Tip	When you're at the grocery store, make the healthiest choice by reading food labels and comparing calories per serving size. When in doubt, choose the option with less calories.
Wednesday	12pm	Weigh Reminder	Wednesday Weigh-day reminder! Time to step on the scale and see what progress you've made.
Wednesday	1pm	Weight Feedback	Great work! This week, you lost 1.5 lb(s). You got this! This week, your goal is to lose another 1-2 lbs.
Wednesday	7pm	Weight Loss Tip	A good way to stay away from food temptations is to be active. Next time you're craving something, go for a run or swim!
Thursday	12pm	Diet Tip	Eventually aim towards having only healthy items stored in your pantry and fridge! Do this by slowly getting rid of unhealthier items and replacing them with better-for-you alternatives.
Friday	12pm	Exercise Feedback	You're more than half way there! Good job getting to 90 active minutes so far. Your goal is to get 130 minutes by Monday, keep on going!
Friday	7pm	Fitness Tip	Do whatever makes exercise most enjoyable for you. Music? A podcast? You are much more likely to exercise consistently if you enjoy it.
Saturday	12pm	Resilience Tip	It's Saturday and time to release some stress! Press two fingers in the center of your other palm and hold for ten seconds.

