## **Comparison Condition**

The comparison condition will also receive a Fitbit Charge 3 and Aria Scale to use at their discretion. This will allow participants to access the Fitbit smartphone application which includes physical activity, dietary and sleep tracking.

The study is implementing mechanisms for preventing comparison group subjects from accessing the intervention components of the SMART 2.0 study. For example, tailored content, goal and behavior feedback, and participant-to-participant and participant-to-health coach interactions will be reserved only for private, invitation-only online groups for participants in the two treatment groups.

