- **Secondary aim analyses:** Secondary aim 1 will be achieved by using the MMRM approach outlined above to compare differences between the SMART 2.0 intervention groups and the control group at 6, 12, 18, and 24 months in anthropometric and physiological outcomes, PA, diet, sleep, body image, anxiety, depression, and the frequency and composition of participant's online communication about weight-related behaviors (all of these measures are continuous). Secondary aim 2 will examine the dose response (i.e., engagement with intervention modalities) of the SMART 2.0 interventions on outcomes at 6, 12, 18, and 24 months. Engagement variables will be included as independent variables in multiple regression models with the study outcomes as the dependent variable adjusting for covariates. Secondary aim 3 will examine the usability and acceptability of the intervention using the framework advanced by Strauss and Corbin. Transcribed audio recordings will be analyzed in three stages: open, axial, and selective coding. During open coding, the data will be examined line-by-line and key concepts and their properties will be discovered. Axial coding involves identifying the relationships among the data, which will then become fully integrated through selective coding. These processes will be documented via memos, which will provide a roadmap of the analytic process. Secondary aim 4 will be accomplished following methods outlined by MacKinnon and Kraemer. We will examine factors that may mediate or moderate the effect of the SMART 2.0 interventions on study outcomes. Mediators (e.g., PA, diet, social support) will inform how the intervention may have worked to change the outcome, while moderators (e.g., sex, age, social network connectivity, contamination) will illuminate for whom and under what conditions the intervention may have been efficacious. Mediation will be tested via path analysis with regression paths from randomized group to change in the mediator and from change in the mediator to change in the outcome, along with a direct path from the intervention to change in the outcome. Adding interaction terms to the models assessing the intervention effects will test moderation. Secondary aim 5 will examine patterns of PA, diet, and sleep as measured over 24 months by Fitbit and MyFitnessPal using Gaussian process regression models. Models will include separate long- and short-term trends for each of the intervention along with common terms for weekly and yearly periodic trends and indicator variables for holidays. We will also use the time-varying effect model to examine how changes in these behaviors over time influence weight. For all secondary analyses of interest, no adjustments for multiple comparisons will be made and a p-value of 0.05 will be considered statistically significant.

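### Secondary aim 5 names MyFitnessPal, which the trial does not provide for collecting, and its Gaussian process model lists no participant-level term

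*Combined protocol and SAP*

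**What the plan says.** Under Overall Approach, the text on secondary aim 5 says that the study will examine "patterns of PA, diet, and sleep as measured over 24 months by Fitbit and MyFitnessPal using Gaussian process regression models". The two sources are named together, without saying which behaviour comes from which. The models are to have "separate long- and short-term trends for each of the intervention along with common terms for weekly and yearly periodic trends", plus indicators for holidays. The passage does not say whether the unit is the person-day or a daily arm mean, and it describes no within-person correlation. Secondary analyses are tested at 0.05 without adjustment.

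Elsewhere the trial's own tools are "a popular consumer-level wearable activity tracker (Fitbit Charge 3), wireless scale (Aria Scale), and apps (Fitbit") (section 8, Overview). The device section adds: "All participants will have the ability to monitor physical activity, sleep and diet with the Fitbit Charge 3". The Comparison Condition section gives the control arm the Fitbit app with its dietary tracking, and Table 7 lists device- and app-based diet as continuous in all participants.

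**The concern.** There are two separate problems. First, an analyst following the aim 5 text would look for a MyFitnessPal dataset that no section of the plan produces. Second, aim 5 rests on long daily series from the same people. The primary model specifies an unstructured covariance for four post-baseline visits per person. Aim 5, with up to several hundred records per person, specifies none. If days from one person are treated as independent, the model takes stable differences between people for information about the arm. The arm curves then look more precise than they are, and they are read against an unadjusted 0.05 level.

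**Working it through.** **Data source.** The places that bear on it, side by side:

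- Overall Approach, aim 5: Fitbit and MyFitnessPal.
- Background and Significance, on the predecessor trial: "Participants in both study groups reported using non-study designed, consumer-level devices and apps to help them meet their weight-loss goals (e.g., Fitbit and MyFitnessPal"). This is the only other mention of MyFitnessPal in the body text, and there it is a non-study app.
- Overview, the wearable and scale section, and Comparison Condition: Fitbit tracker, Aria scale and Fitbit app, with diet tracked in Fitbit in all arms.
- Human Subjects: eligibility requires willingness to use the Fitbit devices and app. No other food-logging app is mentioned.
- Wearable and scale, risk management and privacy sections: device data go from Fitbit through Fitabase to the study servers. No route is given for MyFitnessPal.

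The MyFitnessPal reference therefore conflicts with the rest of the plan, and Fitbit remains as a documented source for diet.

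**Error bands.** The plan gives no figure for aim 5, so there is none to reproduce. Inputs:

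- Follow-up is 96 weeks (Overview): 96 × 7 = 672 daily records per person at most.
- Sleep: 4 nights a week × 96 = 384 nights. The request for four nights is stated for the first week and in a sample message; carrying it through is an assumption.
- Diet, illustrative only: 3 days a month × 24 = 72 days, from one sample message in Table 4.
- Short-term trend: a window of about 14 days is assumed, because the plan gives no length scale.
- ICC, the share of daily variance that lies between people: not in the documents; assumed 0.01 to 0.50.

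For an arm's mean level, with m records per person, the true standard error divided by the naive one is √(1 + (m − 1) × ICC). For m = 672:

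- ICC 0.01: √(1 + 671 × 0.01) = √7.71 = 2.8
- ICC 0.10: √(1 + 671 × 0.10) = √68.1 = 8.3

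| Records per person | ICC 0.01 | ICC 0.10 | ICC 0.30 | ICC 0.50 |
|---|---|---|---|---|
| 672 (daily) | 2.8 | 8.3 | 14.2 | 18.3 |
| 384 (sleep) | 2.2 | 6.3 | 10.8 | 13.9 |
| 72 (diet) | 1.3 | 2.8 | 4.7 | 6.0 |
| 14 (short window) | 1.1 | 1.5 | 2.2 | 2.7 |

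The true coverage of a nominal 95% band is 2Φ(1.96 / ratio) − 1. With 672 records it is 52% at ICC 0.01 and 19% at 0.10. With 72 records it is 87% and 51%.

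A simulation of 182 people (the number needed per group in the sample-size section) over 672 days, with a participant intercept and independent daily errors, gave ratios of 8.3, 14.1 and 18.4 at ICC 0.1, 0.3 and 0.5. Naive coverage was 20%, 10% and 9%. Standard errors computed at participant level brought it back to 94–96%.

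**Limits of this arithmetic.** It covers the level of an arm's curve. Bands for change over time also depend on how far participants' trajectories differ, which the documents do not give; that is the reason for a participant-specific trend as well as an intercept. For balanced within-person contrasts, such as the common weekly and holiday terms, leaving out a participant intercept makes the standard error too wide, by 1/√(1 − ICC), or 1/√0.70 = 1.2 at ICC 0.30.

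**The case against.** The strongest reply is that the aim 5 text is a short summary. It says what the models include and does not exclude a participant term or fix the unit of analysis, so the fair complaint is that the model is unspecified, not that it is wrong. The ICC is assumed, and 672 records require wear on every day. This stands: the narrow bands follow only if person-days are fitted with the listed terms alone. It does not remove the point, because the structure that decides the width of the bands would otherwise be chosen after the data are seen.

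A reader might also infer four stronger things that the documents do not support.

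- *That diet has no data source and cannot be analysed.* The same sentence names Fitbit, and the Fitbit app records diet in every arm.
- *That the bands are 8 to 18 times too narrow throughout.* Those factors belong to an arm's two-year mean with near-daily records and an ICC of 0.10 or more.
- *That diet logging is too sparse for a weekly cycle.* The prompt "Continue to make progress by tracking consecutively for 3 days this month" is one sample message, not a logging schedule. The weekly term is shared across participants, so different people's days can cover the week. Even 72 days from each of the 2 × 214 = 428 intervention participants would be 428 × 72 = 30,816 person-days.
- *That prompted logging in the intervention arms invalidates the arm comparison.* The control arm does use its devices at its discretion ("The comparison condition will also receive a Fitbit Charge 3 and Aria Scale to use at their discretion"). But arm comparisons of activity, diet and sleep are already planned under aim 1 at the scheduled visits, where the measures section provides ActiGraph and ASA24 for all participants. Reporting worn and logged days by arm would be a useful addition, but it corrects no error.

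**Conclusion.** The point holds in two parts. The MyFitnessPal reference conflicts with every description of the trial's tools and data flow; this is a wrong or leftover source name and does not mean that diet data are absent. The Gaussian process model, as described, has no participant-level term and no stated unit of analysis. Fitted to person-days with only the listed terms, it would understate the error of arm levels and arm trends: about 2.8-fold for an arm's overall mean at ICC 0.01 and about 8-fold at 0.10, assuming 672 records per person. With 72 diet records the factors are 1.3 and 2.8, and over a 14-day window 1.1 and 1.5. The direction holds for any positive ICC; the size rests on the assumed ICC and on how often people wear and log. The primary analysis of weight is unaffected.

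**What to change.** In the aim 5 text, replace MyFitnessPal with the Fitbit app food log, or state how MyFitnessPal data would be obtained, from whom and by what route. State that the Gaussian process models are fitted to person-days, and add a participant-level random intercept and a participant-specific smooth trend to the listed arm, periodic and holiday terms. The change needs a few lines of SAP wording and no new data if the Fitbit log is used. The downside is more computing time and wider bands around the arm curves.

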
## 9. HUMAN SUBJECTS

Up to a total of 642 young adults will participate in the proposed research.

**Inclusion criteria:** a) age 18 to 35 years; b) intending to be available for a 24 month intervention; c) affiliated with either UCSD, SDSU or CSUSM as a student, faculty or staff; d) willing and able to use Facebook and follow at least one of study's Facebook, Instagram or Twitter pages; e) willing and able to use a smartphone and text messaging; f) willing and able to use the Fitbit devices and app; g) willing and able to attend measurement visits at UCSD over the 2 year RCT; h) willing and able to engage in moderate to vigorous physical activity; i) overweight or obese, but not severely obese ( $25 \leq \text{BMI} < 40 \text{ kg/m}^2$ ).

**Exclusion criteria:** a) any comorbidities of obesity that require a clinical referral including eating disorders, pseudotumor cerebri, sleep apnea or hypoventilation syndrome, orthopedic problems, and meeting American Diabetes Association criteria for diabetes; b) psychiatric or medical conditions that prohibit compliance with the study protocol; c) had a cardiovascular event (heart attack, stroke, episode of heart failure, or revascularization procedure) within the last 6 months; d) currently being treated for a malignancy (other than non-melanoma skin cancer); e) currently being treated and/or have an eating disorder; f) planning to have a weight loss surgery in the next 24 months (e.g., liposuction, lap band, gastric bypass); g) pregnant, gave birth within the last 6 months, currently lactating or breastfeeding within the last 3 months, or actively planning pregnancy within the next 24 months. This will be determined by participant self-report.; h) prescribed PA and dietary changes; i) prescribed medications that alter weight; j) enrolled in or planning to enroll in a weight loss program during the study period; k) lost more than 15 pounds within the past 3 months.

We will recruit young adults, including students, faculty and staff, from three institutions in San Diego County enrolling approximately 86,000 students and with over 40,000 faculty and staff members. The **University of California, San Diego (UCSD)** enrolls 36,624 students: 28,587 undergraduates (mean age: 21 years), 8,037 graduate students. Undergraduate students are 49.1% female, 37.6% Asian, 19.1% White, 17.8% Mexican-American or Latino, 2.5% African American, with the remainder other or not stated. **San Diego State University (SDSU)** enrolls 33,870 students: 29,513 undergraduates (mean age: X years), 4,357 graduate students (mean age: 22 years). Among all students, 55.1% are female, 13.4% are Asian/ Pacific Islander, 34.7% are White, 28.9% are Hispanic/ Latino, 3.9% are African American, with the remainder as other, multiple ethnicities, or not stated. **California State University, San Marcos (CSUSM)** enrolls 13,893 students (mean age: 22.6 years). Among all students, 61.1% are female, 9.6% are Asian, 27.2% are White, 44.2% are Hispanic/ Latino, 3.0% are African American, with the remainder as other, two or more races or not stated. These campuses enroll a diverse group of students in terms of race, ethnicity and SES background rendering the results of this study generalizable to a broad range of young adults nationwide.

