Subjects assigned to the SMART 2.0 with technology and personal health coaching treatment group (T1) will receive the following during the 24-month (96 week) intervention period: 1) Fitbit Charge 3 activity tracker and Aria scale, 2) daily text messages related to physical activity, diet, sleep and weight loss/maintenance, 3) access to SMART 2.0 social media pages and content through an online group with 6 to 12 participants total, and 4) technology-mediated, real-time individual health coaching. Subjects will receive 1 to 2 text messages on a daily basis, be asked to use their Fitbit on a daily basis and self-weigh using the Aria at least once per week, be asked to interact with their online group via social media as frequently as possible, and speak with their health coach at a predetermined session schedule.

Subjects assigned to the SMART 2.0 technology alone treatment group (T2) will receive the following activities during the 24-month (96 week) intervention period: 1) Fitbit Charge 3 activity tracker and Aria scale, 2) daily text messages related to physical activity, diet, sleep, resilience and weight loss/maintenance, and 3) access to SMART 2.0 social media pages and content through an online group with 12 participants total.

Subjects will receive 1 to 2 text messages on a daily basis, be asked to use their Fitbit on a daily basis and self-weigh using the Aria at least once per week, and be asked to interact with their online group via social media as frequently as possible.

Subjects assigned to the control group will simply receive a Fitbit Charge 3 and Aria scale to use at their discretion.

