## **Intervention Components**

The intervention will be delivered using our four principal intervention modalities: (1) consumer-level wearable and scale (Fitbit Charge 3 and Aria Scale), (2) mobile text messages, (3) online social media pages and groups, and (4) individual health coaching (T1 only). Modalities will incorporate the theory-based behavioral change techniques (BCTs) and strategies for weight management (SWMs) mentioned in Table 1.

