19	Healthy eating on a budget	Learning to make smart, but cost-effective food choices when eating out or shopping at grocery store
20	Getting enough sleep	Ways to get enough sleep with time constraints; Importance of sleep for overall health and weight loss/management
21	Vigorous intensity physical activity	Benefits of VPA; gauging intensity; safety; how to get VPA anywhere

22	Have healthy food you enjoy	Brainstorm enjoyable, healthy options; switching up your meal plan to stay on track
23	Staying active	Tips to stay active while on break/vacation and with schedule constraints; ways to get back on track with exercise
24	Maintaining a healthy lifestyle	Reviewing 6-month progress; seeing what works; identifying barrier and solutions; 6-month goal-setting; planning for next 6-month cycle

In addition to online groups, the health coach will also post general content related to weight loss/management, physical activity, healthy eating, sleep and resilience to the study's various pages on the following commonly used social media platforms: Facebook, Instagram and Twitter. Participants will be required to at least "like" the SMART 2.0 Facebook page and will be encouraged to also "follow" the study's Instagram and Twitter accounts. By "liking" and "following" these respective pages, SMART 2.0 content will appear on their individual social media feeds and participants will be able to "like" and "comment" on each post, communicate with other participants through each post, and "save" any content.

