Numerous privacy issues regarding the use of social networking platforms will be addressed with safeguards at multiple levels throughout the system. We will use Secure Socket Layer (SSL) protocol for communications with the Facebook, Instagram and Twitter servers. Engagement data collected from study's posts on social

media platforms will be collected using Sendible (<https://www.sendible.com/>), a social media management tool. Sendible collects social media reports which aggregates participants' engagement via "likes", "comments" and "shares". In turn, engagement of individual participants will not be collected reducing concerns for privacy.

The study's Facebook, Instagram and Twitter pages will protect user data and honor privacy choices. Participants will be issued guidelines as to appropriate information to publish and reveal on the social media pages and within their online groups. To ensure that all participants are aware of Facebook, Instagram and Twitter privacy policies and how they can control and/or change their privacy settings, each participant will be provided with a handout prior to the start of their participation in the study on how to set their privacy preferences. The SMART Health Coach will be a "friend" of all participants on Facebook in order to invite them to online groups on Facebook messenger. The Health Coach will monitor the Facebook, Instagram and Twitter study pages and each Facebook Messenger group and alert participants to any observed privacy risks.

Risks of anxiety, embarrassment, or feelings of inadequacy during the measurement process will be minimized by fully informing participants of the study procedures and explaining that they may refuse to participate or stop participation at any time if they are unable to complete a laboratory test. Participants will also be informed that the Fitbit Charge 3 is not considered to be a medical device or a significant risk device. Physical discomfort from wearing the devices will be minimized by providing instructions on how best to wear the Fitbit Charge 3 and study staff will be present to make any necessary adjustments.

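### The protocol does not keep the control arm off the study's social-media pages, which it defines as a component for T1 and T2 only

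*Combined protocol and SAP*

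**What the plan says.** In section 8, Intervention Components and Standardizing Delivery of the Intervention both list "online social media pages and groups" as one of four modalities. The Overview gives page access to T1 and T2, and says of the third arm: "Subjects assigned to the control group will simply receive a Fitbit Charge 3 and Aria scale to use at their discretion".

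Comparison Condition states: "The study is implementing mechanisms for preventing comparison group subjects from accessing the intervention components of the SMART 2.0 study". Its example is that, along with tailored content and feedback, "participant-to-participant and participant-to-health coach interactions will be reserved only for private, invitation-only online groups" for the two treatment arms. The pages are not mentioned.

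Four other places bear on the pages:

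- Online Group/Social Media (text after Table 5): the coach posts general weight-related content on the pages, participants must at least like the Facebook page, and followers can "communicate with other participants through each post". No arm is named.
- Section 9, criterion (d): each enrollee must be "willing and able to use Facebook and follow at least one of study's Facebook, Instagram or Twitter pages".
- Section 14: the coach will be a friend "of all participants on Facebook in order to invite them to online groups on Facebook messenger".
- Engagement with Intervention Modalities, Table 7 and the secondary aim 4 analysis: contamination is expected, is listed as a measure at every visit, and is to be explored as a moderator.

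**The concern.** All three arms receive the tracker and scale. T2 therefore differs from control only by text messages and social media, and the pages belong to one of those two distinguishing modalities. If controls follow the pages, they receive part of what the trial is testing. Both primary comparisons (T1 with control, T2 with control) use the same control arm, so both would be pulled toward zero together. The primary analysis in Overall Approach is by intention to treat and has no term for this. Power and Sample Size makes no allowance for it.

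**Working it through.** **Step 1: set the texts side by side.**

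| Question | Protocol text | Does it protect controls? |
|---|---|---|
| Are the pages an intervention component? | Yes (Intervention Components; Overview, T1 and T2) | Controls should be kept off |
| What barrier is stated? | Private groups only, given as an example (Comparison Condition) | Pages not covered |
| Can participants interact on the pages? | Yes (Online Group/Social Media) | Conflicts with reserving interaction for private groups, whichever arms use the pages |
| Who must be willing to follow? | Every enrollee, confirmed before randomization (sections 9 and 10) | Not tied to assignment |
| Whom does the coach friend? | All participants, for the purpose of group invitations (section 14) | Literal wording includes controls |
| Are controls told not to follow, or are the pages closed to them? | Not stated | No |

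**Step 2: would the planned measurement capture control exposure?** Only in part. Engagement with Intervention Modalities restricts the quantitative markers to intervention participants and gives controls the questionnaire on device and app use. Online ties are collected only as platform rules permit. Section 14 says the page-management tool will not collect engagement of individual participants.

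**Step 3: reproduce the sample size.** Inputs from Power and Sample Size: difference 1.60 kg, SD 4.92 kg, two-sided alpha 0.025, power 80%.

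- Normal approximation: n = 2 × (2.2414 + 0.8416)² × (4.92/1.60)² = 2 × 9.505 × 9.456 = 179.8, so 180 per group.
- Two-sample t-test: 181.01, so 182 per group, as stated.
- Attrition: 182/0.85 = 214.1. The plan's 214 gives 214 × 0.85 = 181.9 evaluable, and 3 × 214 = 642.

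The stated figure reproduces on its own inputs.

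**Step 4: sensitivity to a smaller contrast.** Let f be the share of the 1.60 kg lost through control exposure. The documents give no value for f, so it is an assumption. The standard error is 4.92 × √(2/182) = 0.516 kg, and approximate power is Φ(1.60(1 − f)/0.516 − 2.2414). The t-test values are:

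| Assumed f | Difference (kg) | Power at 182 per group | Evaluable per group for 80% | Total randomized at 15% attrition |
|---|---|---|---|---|
| 0 | 1.60 | 80.2% | 182 | 642 (as planned) |
| 5% | 1.52 | 75.7% | 201 | 711 |
| 10% | 1.44 | 70.6% | 224 | 792 |
| 20% | 1.28 | 59.2% | 283 | 999 |
| 30% | 1.12 | 46.9% | 369 | 1305 |

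The last column rounds n/0.85 up per group and multiplies by three. For example, 224/0.85 = 263.5, so 264, and 3 × 264 = 792.

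**The case against.** A reader might infer that controls will be on the pages because every enrollee must agree to follow one. The documents do not say that. Criterion (d) is a willingness condition checked before randomization, when each person must be prepared to accept any arm. Criterion (e), on smartphone and text-message use, works the same way, and the study's text messages still go only to T1 and T2.

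The coach's friending is tied to invitations to groups that only T1 and T2 have, and Online Group/Social Media describes it directly after those arms are placed in groups. The required like sits within the description of an intervention component. The barrier in Comparison Condition is introduced as an example, so it need not be the only one.

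The page content is general. Tailoring, text messages, private groups and coaching remain closed to controls. The plan also openly expects contamination and intends to measure and explore it.

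On size, no figure in the documents supports any value of f. The 1.60 kg target was scaled up from a predecessor result of 1.33 kg, in a trial where 56% of participants had a Facebook friend in the study, so some cross-arm contact may already be in that benchmark.

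Most of this stands, and it limits the point to possible exposure of unknown size. It does not remove the gap. Staff who follow sections 9 and 14 as written could friend controls and let them follow the pages. Exploring contamination as a secondary, post-randomization moderator does not restore a primary contrast that has already been diluted.

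**Conclusion.** The protocol promises to keep controls off the intervention components but states no barrier for the pages, and its wording on following and friending is not limited by arm. The conflict is in the text and depends on no assumed number. That controls are exposed, or that the contrast is diluted by any given amount, is not established. Dilution would require that controls do follow the pages and that general posts affect weight as intended.

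The power figures show only that the design has almost no slack: about 80% as planned, about 71% at an assumed 10% loss and about 59% at 20%, with SD and evaluable numbers held at the plan's values. The point is worth acting on because prevention is cheap and no planned analysis removes the effect afterwards.

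**What to change.** 1. Section 14: limit coach friending to T1 and T2.
2. Online Group/Social Media: state that the required like and the encouraged follows apply to T1 and T2 only.
3. Criterion (d): make willingness to follow conditional on being assigned to T1 or T2.
4. Comparison Condition: extend the barrier to the pages by asking controls not to follow them, and restrict page access after randomization where the platform allows. Reconcile the statement that interaction is reserved for private groups with the commenting allowed on the pages.
5. Log control accounts that follow a page or are tied to the coach, so that any exposure can be reported.

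The cost is protocol wording and a short IRB amendment. Restricting the pages would lose some public reach and sharing, and the intervention relies partly on support from outside the study. Full closure of all three platforms is therefore optional; the other changes do not depend on it.
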